## **7 Quantitative Data Analysis**

### **7.1 Cross-sectional study**

Analytical approaches to the analysis of data from the prevalence study will focus on univariate summaries but will also investigate risk factors for deferral. An exact

confidence interval for the probability of deferral will be computed using the method first described by Clopper and Pearson. Logistic regression will be used to assess risk factors for deferral. These risk factors will include age, sex, previous donation status and type of donor.

Since recruitment at donation events focuses on informing individuals who fail the copper sulphate test about the study, we expect that the proportions of those who are ID and IDA will be higher than the proportion among those attending a donation event. For this reason, we will estimate the level of ID and IDA overall by weighting the estimates within deferral strata by the observed probability of deferral based on the cross-sectional study of deferral (but restricted to first time donors, or voluntary first time donors depending on who enrolls into the ID/IDA study). To obtain 95% confidence intervals for the overall proportion of those who are ID and IDA we will use a Bayesian approach in which we sample the probability that first-time donors are deferred for low haemoglobin from its posterior distribution (which is a beta distribution) and we sample the probability of being ID and IDA conditional on deferral status from their posterior distributions (which will also be beta distributions). We can then combine these draws from the posterior distributions to obtain weighted estimates of the probability of being ID and IDA that will be consistent for these probabilities in the overall population. Risk factors for being ID and IDA conditional on the outcome of the copper sulphate test will be examined using logistic regression.

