Out of the sampling frame, participants will be purposively sampled for Focus Group Discussions (FGDs). In all there will be ten FGDs i.e. two groups (male-only and female-only) randomly selected to represent each of the five NBSG voluntary blood donation categories (excluding mass/media event donors), and with each group composed of both first-time and repeat donors. In-depth interviews will also be conducted with blood donation staff and medical officers responsible for blood donation.

Regimen

The prevalence study will be conducted over the first 6 months of the study period. For the cross-sectional deferral assessment, all donation attempts and deferrals from sites where recruitment for the parallel groups study will take place will be recorded. The number of deferrals among first-time donors will also be determined. Potential first-time donors will be asked if they are interested in participating in a study of the prevalence of ID and IDA and the impact of iron supplementation on haemoglobin levels and repeat donation. Those who express interest and consent to the study will be asked to return in approximately 2 weeks. During this 2-week period a full blood count (FBC) and plasma ferritin measurement will be determined, and participants will be classified as ID, IDA or otherwise (which we refer to as controls in this protocol). Those found to be ID or IDA will receive oral

iron supplementation and nutritional counseling. Controls will not be given iron supplementation but will receive the standard practice of nutritional counseling for blood donors. Additional baseline data will be collected at the 2-week return visit. The duration of the intervention period is 4 months with two interim visits (approximately 2 months apart) and a final visit at 6 months. A blood draw will be conducted for a FBC, peripheral film comment, malaria rapid test and ferritin measurement at both interim visits and the final visit. Participants will receive bi-weekly follow-up phone calls for adherence and monitoring for adverse events. Qualitative assessment of acceptability of oral iron supplementation among donors previously deferred will be performed during the final month of the pilot study.

Inclusion Criteria

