The parallel group's component is designed as a non-inferiority trial for haemoglobin levels at 4 months. At baseline, the 2 groups will be determined based on the need for iron supplementation: all individuals with ID, IDA or low haemoglobin (gender specific values), who satisfy our eligibility criteria regardless of deferral status, will receive iron supplements while all others will not. While a high prevalence of ID and IDA is expected, enrolment will be staggered so that an equal number of participants from each group are enrolled from each site with at least 1 participant who is assigned to iron supplementation. If there are more potential participants in one group at some site, randomization will be used to select the individuals to enroll in the trial to maintain balance over time. The extent of adherence is a central question for this study, and it is also unclear if the haemoglobin deficiency can be improved above what is seen in the control group, hence it is not hypothesized that those receiving iron supplementation will have higher levels of haemoglobin at 4 months. The hypothesis about the iron supplementation intervention is that it will improve haemoglobin levels to near that seen among those who did not receive iron supplementation. If haemoglobin levels are higher in those receiving iron supplementation the intervention would also be deemed a success. Hence a non-inferiority trial is most appropriate for this hypothesis.

Selection of the margin is a critical component of a non-inferiority trial. Here, we specify a margin of 1 g/dL for haemoglobin levels at 4 months. Under a collection of reasonable assumptions, this margin will ensure that the majority of those with low haemoglobin at screening will have haemoglobin levels at 4 months above the threshold for anaemia and should therefore qualify as donors. To see this, assume that half of donors are anaemic at screening (using the thresholds for anaemia of 13 g/dL for men and 11.5 g/dL for women). A simple calculation finds that if we assume haemoglobin levels are normally distributed (which is a reasonable assumption based on observed distributions for haemoglobin in unselected individuals in West Africa) and the standard deviation of screening haemoglobin levels is 1.89 g/dL (this estimate will be described below) then the mean haemoglobin level among men who are deferred is 11.5 g/dL and the mean haemoglobin level among men who are not deferred is 14.5 g/dL (these values for

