## Sample size

**Qualitative study:** In all, ten focus groups of 8-10 participants purposively selected with one group from each of the following blood donation categories: (i) religious organizations, (ii) educational institutions, (iii) corporate institutions, (iv) organized community groups, and (v) walk-in blood donors. The aim of the focus groups is to identify barriers and recommendations for using iron supplementation and nutritional counselling to increase the blood donor pool. These discussions may involve gender-sensitive topics and gender may impact participation in the discussion, so two groups of each blood donation category by gender will be formed (e.g., 8-10 females, 8-10 males). The female and male focus groups will meet in separate spaces so only one gender will be interviewed at a time. Thus, there is one male and one female group for each donation category.

**Quantitative method:** Cross-sectional study to determine the prevalence of anaemia among prospective blood donors: There are 2 distinct components of the cross-sectional study: estimation of the proportion of potential donors deferred due to low haemoglobin and the proportion of first-time potential donors who have ID and IDA. The determination of deferral due to low haemoglobin is routinely collected by the National Blood Service Ghana (NBSG) and does not require consent of potential donors in this study. The proportion deferred will be determined using the same donation sites as the other components of the study with an estimated sample size of 600 and resulting margin of error less than 0.04. Consequently, the 95% confidence intervals for deferral prevalence will have a total width of less than 0.08 giving a more precise estimate than the year-to-year variation in the total percentage deferred. Participant consent is needed to draw blood for determination of ID and IDA. We anticipate that 292 participants will consent and be enrolled with resulting margin of error less than 0.057 and total confidence interval width of less than 0.11 for likely values of the prevalence of ID and IDA among first-time potential donors (conditional on deferral status). Thus, the ID and IDA prevalence estimates will have comparable precision to the estimated proportion of those deferred using all potential donors at recruitment sites.

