## **Study site and Population**

The NBSG SZBC located in the capital Accra annually collects voluntary blood donations from 200-300 blood donor groups that are categorized as (i) religious organizations, (ii) educational institutions, (iii) corporate institutions, (iv) organized community groups, (v) walk-in blood donors and (vi) mass/media events. Data for the prevalence of deferral assessment will be collected from all prospective voluntary blood donors within the catchment areas of the SZBC. The prevalence study of ID and IDA as well as the parallel groups trial will be restricted to first-time donors. The parallel groups trial will be restricted to voluntary donors. Generally, prospective voluntary blood donors are healthy, unlikely to be severely anaemic and are more likely to be male.

The study population will be all adults between the ages of 17 and 60 years who visit blood donation sites at the time of recruitment. A stringent screening and selection process is performed to evaluate the suitability of prospective donors. This is essential to guarantee the safety and adequacy of the blood supply; protecting the wellbeing of the recipients of transfusion as well as the fitness of the donors while ensuring that qualified donors are not deferred needlessly.

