## **Stratification and Sampling**

The SZBC contributes to the blood service needs of the Western, Central, Greater Accra, Eastern and the Volta Regions of Ghana. In 2018 and 2019, the SZBC attended to an average of 550 prospective voluntary blood donors a week, including 80 walk-in donors. Out of this number, the study will recruit all participants (who fall within the inclusion criteria) reporting per day for up to 6 months until the sample size is attained. Eligible participants will form the sampling frame for the study.

Donors will be informed about the trial and the prevalence study of ID and IDA. Due to a need to recruit approximately equal numbers of participants in the 2 groups in the trial, donors who fail the copper sulphate test will be disproportionately approached for participation. This creates a stratification of donors by status with regard to the outcome of the copper sulphate test. Within these strata the proportion of donors who are ID and IDA will be determined. The estimates of these proportions within strata will be unbiased but if one simply averages over the strata, we expect that the estimates of the proportion who are ID or IDA will have positive bias. However, since we will have estimates of the proportion of donors who fail the copper sulphate test, we can post-stratify the proportions of donors who are ID or IDA by the proportion of donors who fail the copper sulphate test.

Out of the sampling frame, participants will be purposively sampled for FGDs. In all there will be ten FGDs i.e., two groups (male-only and female-only) selected to represent each of the five NBSG voluntary blood donation categories (excluding mass/media event donors), and with each group composed of both first-time and repeat donors. In-depth interviews will also be conducted with blood donation staff and medical officers responsible for blood donation.

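### Donors are recruited by site, event and donor group, but the deferral, ID and IDA intervals assume independent donors, so they are too narrow to the extent that prevalence varies between sessions

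*SAP*

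**What the plan says.** **How donors reach the study.** The blood centre "annually collects voluntary blood donations from 200-300 blood donor groups", sorted into six categories (SAP 1.2, Study site and Population). It sees "an average of 550 prospective voluntary blood donors a week, including 80 walk-in donors" (SAP 1.2, Stratification and Sampling). For deferral, the SAP states: "The proportion deferred will be determined using the same donation sites as the other components of the study with an estimated sample size of 600" (SAP 1.2, Sample size). The Protocol (Regimen) agrees: "all donation attempts and deferrals from sites where recruitment for the parallel groups study will take place will be recorded". The ID/IDA sample is also taken at events: "Since recruitment at donation events focuses on informing individuals who fail the copper sulphate test about the study" (SAP 7.1).

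**How the data are analysed.** For deferral, the "confidence interval for the probability of deferral will be computed using the method first described by Clopper and Pearson". For ID and IDA, SAP 7.1 draws the deferral probability and the stratum-specific probabilities from beta posteriors and combines them, weighting by deferral status only. The logistic model for deferral uses age, sex, previous donation and type of donor. SAP 3.4 shows that donation type means replacement/family or voluntary, not donor group. Tables 1 and 2 (SAP 2.4) use the normal approximation for a single proportion.

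**Elsewhere.** In SAP 7.2.2 the incidence model treats different participants as independent, and the longitudinal models allow only for repeated measurements on one participant. Neither document contains a design effect, an ICC, or a site or session term.

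**The concern.** Clopper-Pearson and independent beta posteriors are correct when each donor is an independent draw from the target population. Here whole sessions enter together: a congregation, a school, a company or a community group. If such groups differ in sex mix, age or diet, two donors from one session are more alike than two donors from different sessions. The sample then carries less information than its head count suggests.

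Prevalence is the aim of two of the three study components, and SAP 2.4 justifies n = 600 by the ability to compare the estimate with yearly deferral figures. An interval that is too short would overstate that ability. Logistic standard errors for risk factors shared within a session would tend to be too small for the same reason.

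The SAP already corrects for one departure from simple sampling, the over-recruitment of donors who fail the copper sulphate test, but post-stratifying by deferral status does nothing about clustering.

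**Working it through.** **1. Reproduce the plan's margins.** Formula: margin = 1.96 × √(p(1−p)/n), with p = 0.5.
- Deferral, n = 600: 1.96 × √(0.25/600) = 0.0400. Table 1 gives 0.040.
- ID/IDA, n = 292: 1.96 × √(0.25/292) = 0.0573. Table 2 gives 0.057.

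The other rows of both tables also reproduce. The figures are arithmetically right for independent donors.

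**2. Is it a sample of sites or a census?** At 550 donors a week, 26 weeks bring 550 × 26 = 14,300 attempts. The plan expects about 600, and 600/14,300 = 4.2%. Which sites contribute is therefore part of the sampling error.

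**3. Allow for clustering.** Design effect DEFF = 1 + (m − 1) × ICC, where m is donors per session. The adjusted margin is the simple margin × √DEFF. Both m and ICC are assumptions. The value m = 5 echoes the 5 attempts per business day in SAP 2.4, and m = 20 is a moderate donation drive. ICC is taken as 0.01, 0.02 and 0.05. Coverage is for the unadjusted Clopper-Pearson interval at n = 600, from 20,000 beta-binomial simulations.

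| m | ICC | DEFF | Margin, n = 600 | Coverage | Margin, n = 292 |
|---|---|---|---|---|---|
| 5 | 0.01 | 1.04 | 0.041 | 95.1% | 0.058 |
| 5 | 0.02 | 1.08 | 0.042 | 94.4% | 0.060 |
| 5 | 0.05 | 1.20 | 0.044 | 93.0% | 0.063 |
| 20 | 0.01 | 1.19 | 0.044 | 93.0% | 0.063 |
| 20 | 0.02 | 1.38 | 0.047 | 90.9% | 0.067 |
| 20 | 0.05 | 1.95 | 0.056 | 84.7% | 0.080 |

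With n held at 600, the m = 5 rows mean 120 sessions and the m = 20 rows mean 30.

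**4. Is a positive ICC plausible?** The Protocol (Problem Statement) cites anaemia in 42.4% of women of reproductive age and 18.8% of peri-urban men. Suppose the female share varies between donor groups with SD s (an assumption), around an equal mix, so that overall p = (0.424 + 0.188)/2 = 0.306. Then ICC = (0.424 − 0.188)² × s² / (0.306 × 0.694).
- s = 0.1: 0.0557 × 0.01 / 0.2124 = 0.003.
- s = 0.3: 0.0557 × 0.09 / 0.2124 = 0.024.

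This counts sex mix only. The value 0.05 lies above this range and is an upper assumption.

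**5. The post-stratified ID interval.** Illustrative inputs, all assumed: 43% deferred, ID in 60% of deferred and 25% of other donors, 146 per stratum. The 95% interval has width 0.108 at DEFF 1, 0.129 at DEFF 1.45 (m = 10, ICC 0.05) and 0.150 at DEFF 1.95 (m = 20, ICC 0.05). The ratios 1.19 and 1.39 are close to √1.45 = 1.20 and √1.95 = 1.40, so this interval is affected in the same way.

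**The case against.** **The size cannot be read from the documents, and it may be small.** This stands. With 5 donors per session and an ICC of 0.01, Clopper-Pearson, which is slightly conservative, still covers about 95%. An unconditional claim of under-coverage would be wrong.

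**A reader might infer much larger sessions.** Dividing group donors by groups gives (550 − 80) × 52/300 = 81 to (550 − 80) × 52/200 = 122, which suggests sessions of 50 to 100 and margins of 0.049 to 0.098 at n = 600. The documents do not support this, for two reasons.
- The 81 to 122 is donors per group per year, not per session. It also includes mass/media events, and the number of visits per group is not given.
- The 600 follows from 5 attempts a day over 600/5 = 120 days, so larger sessions would raise n. At one session a day and ICC 0.05, m = 50 gives n = 6,000, DEFF 3.45 and margin 1.96 × √(0.25 × 3.45/6,000) = 0.0235. With m = 100, n = 12,000 and DEFF 5.95, the margin is 0.022. Both are below 0.04.

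The same caution applies to the m = 20 rows, which need n to stay near the planned 600. A larger n restores precision but not coverage, because the reported interval is still too short by the factor √DEFF.

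**This is not a formal cluster sample.** The plan takes all eligible donors who report, and 80/550 = 14.5% are walk-ins. One sentence (SAP 1.2, Study site and Population) even reads as if deferral were recorded across the whole catchment. However, the sample-size text and the Protocol's Regimen section confine it to recruiting sites, with about 600 attempts expected. Walk-ins weaken the clustering but do not remove it.

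**A reader might extend the point to the trial's primary model, which has no site term.** That is not supported. Enrolment is planned so that "an equal number of participants from each group are enrolled from each site" (SAP 1.2, Design). With the two groups balanced within site, omitting site need not make the group comparison anti-conservative, and no harm to that test has been shown.

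**Conclusion.** The point holds in conditional form. Recruitment is by site, event and donor group, every interval and model in SAP 7.1 assumes independent donors, and nothing in either document corrects for it. The direction is certain if prevalence varies at all between sessions. The size is not known.

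Under the stated assumptions, the effect on the deferral interval runs from negligible (5 per session, ICC 0.01) to material (20 per session, ICC 0.05, where the margin is 0.056 against 0.040 and coverage is about 85%). No larger figure is claimed. No printed figure is arithmetically wrong. The margins in Tables 1 and 2 simply carry an unstated condition of no clustering. The point concerns the prevalence components only. It is worth acting on because the change is cheap and because clustering cannot be examined later if the session is not captured.

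**What to change.** - **Data.** Add venue and date to the deferral and ID/IDA data sets. Both are on the blood service's donor clinical record reproduced in the Protocol's appendices. Neither is in SAP 3.4, which limits the deferral study to age, sex, previous donation and donation type.
- **Reporting.** Give the number and size of sessions and the estimated ICC for deferral, ID and IDA.
- **Deferral interval.** Use a design-adjusted interval, for example Clopper-Pearson on the effective sample size n/DEFF, or a logit interval with cluster-robust variance.
- **ID/IDA interval.** Keep the post-stratification, but obtain the interval by resampling sessions or from a hierarchical beta-binomial model.
- **Risk-factor models in SAP 7.1.** Use standard errors clustered on session.
- **Tables 1 and 2.** State that the margins assume no clustering.

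The cost is one or two extra variables, some SAP wording and possibly wider intervals. If the ICC proves close to zero, the intervals will barely change. Deferral data are collected without individual consent, so the sponsor should confirm that the approvals cover venue and date. SAP 1.1 allows updates until database lock. The primary model stays as it is.
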